## 6 PROCEDURES

### 6.1 Randomization Procedures

Patients will be randomized 3:1 to receive CM4620-IE in addition to supportive care consistent with the [2013 IAP/APA](#) evidence-based guidelines for the management of acute pancreatitis versus supportive care alone. Randomization will be stratified by sex. CalciMedica or its designee will prepare the randomization schedule prior to the start of the study.

### 6.2 Discontinuation and Withdrawal

Discontinuation refers to the patient or PI discontinuing the administration of CM4620-IE before all 4 doses are administered despite the patient remaining in the hospital. Patients have the right to discontinue the administration of CM4620-IE at any time for any reason, without prejudice to their medical care. The PI may discontinue the administration of CM4620-IE because of an adverse event or change in medical status that raises a safety concern about the patient receiving additional doses of CM4620-IE. The PI **must** discontinue the administration of CM4620-IE if the patient is diagnosed with a new or recurrent malignancy, or if the patient was concomitantly administered a prohibited medication. If possible, the PI should contact the Medical Monitor to review the reasons for a patient's discontinuation from study drug. The PI should also record the reason for the discontinuation in the eCRF and appropriate source documents at the site. Even if the patient discontinues receiving CM4620-IE, diligence should occur to ensure that all study visits and assessments are completed.

Withdrawal refers only to the complete withdrawal of the patient from the study because of the withdrawal of consent. The PI should inform the Medical Monitor of the withdrawal of consent and record the withdrawal of consent in the eCRF and appropriate source documents at the site.

## 7 CM4620-IE MATERIALS AND MANAGEMENT

### 7.1 CM4620-IE Product Description

CM4620-IE is to be administered as an IV infusion and is supplied as a translucent, white to yellowish colored, sterile, non-pyrogenic emulsion containing 1.6 mg/mL of the active pharmaceutical ingredient CM4620. CM4620-IE is supplied as an 80 mL fill in a 100 mL, single-use glass vial. The drug product is formulated as an emulsion due to the low solubility of CM4620 in aqueous solution. CM4620-IE contains egg phospholipids, medium chain triglycerides, glycerin, edetate disodium salt dehydrate (EDTA), sodium hydroxide (as needed to adjust pH), and sterile water for injection (Table 3)

**Table 3 CM4620-IE Product Information**

Product Name:	CM4620 Injectable Emulsion
Dosage Form:	Injectable Emulsion (Liquid)
Concentration	1.6 mg/mL
Route of Administration	IV
Physical Description	Translucent, non-separated, white to yellowish emulsion
Inactive Ingredients	Sterile Water for Injection USP, Egg Phospholipid NF (80% Phosphatidylcholine), Medium Chain Triglycerides NF, Glycerin USP, and Edetate Disodium Salt Dihydrate (EDTA) USP. Sodium Hydroxide and Hydrochloric Acid may be added to adjust the pH.
Manufacturer	Bioserv Corporation San Diego, CA 92121

### 7.2 CM4620-IE Storage

CM4620-IE must be maintained in a secure location with refrigerated temperature conditions of 2 to 8°C (36 to 46°F). Precaution should be taken to ensure that the CM4620-IE does not freeze. Temperature logs should be maintained and available at each monitoring visit. When a temperature is noted outside the temporary excursion range of 2°C to 8°C for 24 hours or more, or if the temperature exceeds 20°C (68°F), or is below 0°C (32°F), CalciMedica or its designee must be notified. The stability of CM4620-IE has been demonstrated to 12 months and is being evaluated for longer periods in ongoing studies.

### 7.3 CM4620-IE Preparation

The study pharmacist and/or designee will be responsible for the preparation and dispensation of CM4620-IE. Prior to administration, CM4620-IE must be transferred to a sterile container a using sterile technique. Specific details on how to calculate and prepare CM4620-IE, as well as the specific components that will be used to administer CM4620-IE, will be provided in a Pharmacy Manual. The Pharmacy Manual will also contain tables detailing the Volume to Be

Infused (VTBI) of CM4620-IE that is based upon the body weight of the patient, the selected dose level, and the concentration of CM4620-IE (1.6 mg/mL).

## **7.4 CM4620-IE Administration**

CM4620-IE will be administered intravenously over 4 hours at a constant rate of infusion. CM4620-IE shall be administered every 24 hours ( $\pm$  1 hours) for a total of 4 doses. The dose of CM4620-IE that will be administered will be calculated using the patient weight obtained at Screening. A line into a peripheral or central vein may be used for the infusion. The peripheral IV should be 20 gauge in size or larger. The peripheral IV or central line port should be dedicated, i.e., only for the administration of CM4620-IE and 0.9% normal saline. CM4620-IE is compatible with 0.9% normal saline. The IV tubing used to administer CM4620-IE must contain a 1.2 micron filter. The Pharmacy Manual will contain a recommended procedure to prime the IV tubing and flush the tubing, but this may be adapted to local nursing standards. 0.9% normal saline may be used to flush the line to ensure that the VTBI is completely administered. If the administration of CM4620-IE is stopped because of a technical reason, such as failure of the IV site, or IV pump malfunction, the administration of CM4620-IE should be resumed when the technical reason is resolved, and continued at the same rate until the infusion is completed. The total amount of time for the start of infusion to end of infusion of CM4620-IE should be recorded.

CalciMedica may modify at any time the administered doses of CM4620-IE, the days of infusion, the timing of the infusion and the rate of infusion based on its review of the safety and tolerability data. CalciMedica will discuss with the PIs before implementation. If the administration of CM4620-IE is stopped because of a serious adverse event that is considered to be probably or definitely related to CM4620-IE, the Medical Monitor must be immediately contacted.

## **7.5 Packaging and Labeling**

Preparation, packaging and labeling of CM4620-IE will be in accordance with current Good Manufacturing Practice of Medicinal Products (GMP) guidelines. Medication labels will comply with legal requirements for labeling of investigational products in the United States.

## **7.6 Accountability, Handling and Disposal**

The PI or designee will ensure that deliveries of CM4620-IE from CalciMedica or its designee are received by a responsible person, and such deliveries are recorded; that CM4620-IE is handled and stored safely and properly; that CM4620-IE is only dispensed to study patients in accordance with the protocol; and that unused CM4620-IE is returned to CalciMedica or its designee or disposed of using standard procedures approved of in advance by CalciMedica or its designee. Appropriately trained study staff will administer all doses of CM4620-IE. The pharmacy will maintain a record of CM4620-IE accountability.

## 8 VISITS AND ASSESSMENTS

### 8.1 Screening

The PI or designee must provide informed consent to the patient, or LAR, allowing the patient or LAR adequate time to consider, ask questions and receive answers, prior to agreeing to participate.

- Record the time of the onset of abdominal pain
- Record the time of the patient or LAR provides informed consent

After informed consent is obtained, the following procedures are to be performed:

- Record demographics and medical history, including medication history
- Record vital signs, height and weight
- Perform a limited physical examination
- Draw serum pregnancy test if the patient is a woman of child bearing potential – analyze at local lab
  - If already performed as part of standard of care, record results
- Draw a blood sample for serum amylase and lipase—analyze at local lab;
  - If already performed at local lab as part of standard of care for the evaluation of abdominal pain, record results
- Draw a blood sample for CBC, differential, and platelets—analyze at local lab
  - If already performed at local lab as part of standard of care for the evaluation of abdominal pain, record results
- Determine if SIRS is present
- Record the SpO2 and the FiO2 and time performed
- In patients who have SIRS and a SpO2 <96% with a FiO2 of 21% (room air) to 27% or a SpO2 <97% with a FiO2 ≥28%, obtain a CECT of the pancreas, or review one performed as standard of care in the 18 hours prior to consent, to determine if pancreatic necrosis is present. The Screening CECT may have been performed more than 18 hours prior to consent and not repeated after consent for patients-specific safety considerations.

If the patient satisfies all of the inclusion criteria and none of the exclusion criteria, immediately proceed to Day 1.

### 8.2 Day 1 (0 hour to < 24 hours)

Perform the following procedures immediately prior to randomization of female patients into Cohort 1 (Cohort 3 during the second phase), and the randomization of male patients into Cohort 2 (Cohort 4 during the second phase):

- Record vital signs

- Record concomitant medications
- Draw a blood sample for CBC, differential and platelets, Chemistry Profile, serum biomarkers—send to central lab
- Obtain a urine sample for biomarker testing—send to central lab
- Record SpO2 and the FiO2 and time performed
- If an ABG has already been performed as part of standard of care, record the pH, PaCO2, PaO2, SaO2 and the FiO2 at the time of draw
- Calculate the Glasgow Coma Scale score
- Record patient's pain using the PNRS
- Assess pain using the CPOT
- **Randomize patient**

If the patient has been randomized to receive CM4620-IE:

- **Start the administration of CM4620-IE (1st dose) as soon as possible after randomization and preferably within 6 hours (up to 8) from the time the patient or legal representative signed the informed consent;**
- If the administration of CM4620-IE is started more than 8 hours from the time the patient or legal representative provided informed consent, note the time and inform the Medical Monitor;
- Draw a blood sample for PK 30 minutes ( $\pm 15$  minutes) after completing the administration of CM4620-IE—send to central lab
- Draw a blood sample for PK 8 hours ( $\pm 30$  minutes) after completing the administration of CM4620-IE—send to central lab

For all patients, at 12 hours ( $\pm 1$  hour) from time of randomization:

- Record vital signs
- Draw a blood sample for CBC, differential and platelets—send to central lab
- Perform an AE/SAE assessment

### **8.3 Day 2 (24 hours to <48 hours)**

For all patients, at 24 hours ( $\pm 1$  hour) from time of randomization:

- Record vital signs
- Record concomitant medications
- Draw a blood sample for CBC, differential and platelets, chemistry profile, serum biomarkers—send to central lab

- Obtain a urine sample for biomarkers—send to central lab
- Record SpO2 and the FiO2 and time performed
- Calculate the Glasgow Coma Scale Score
- Record patient's pain using the PNRS
- Assess pain using the CPOT
- Perform AE/SAE assessment

For patients randomized to receive CM4620-IE:

- Start the administration of CM4620-IE (**2nd dose**) 24 hours ( $\pm$  1 hour) from the start of dose administration on Day 1
  - Draw a blood sample for PK 30 minutes ( $\pm$ 15 minutes) prior to starting the administration of CM4620-IE—send to central lab

For all patients, at 36 ( $\pm$ 1 hour) hours from the time of randomization:

- Record vital signs
- Draw a blood sample for CBC, differential and platelets—send to central lab

#### **8.4 Day 3 (48 hours to < 72 hours)**

For all patients, at 48 hours ( $\pm$ 1 hour) from the time of randomization:

- Record vital signs
- Record concomitant medications
- Draw a blood sample for CBC, differential and platelets, chemistry profile, serum biomarkers—send to central lab
- Obtain a urine sample for biomarkers—send to central lab
- Record SpO2 and the FiO2 and time performed
- Calculate the Glasgow Coma Scale Score
- Record patient's pain using the PNRS
- Assess pain using the CPOT
- Perform AE/SAE assessment

For patients randomized to receive CM4620-IE:

- Start the administration of CM4620-IE (**3rd dose**) 48 hours ( $\pm$ 1 hour) from the start of dose administration on Day 1

For all patients, at 60 hours ( $\pm 1$  hour) from the time of randomization:

- Record vital signs
- Draw a blood sample for CBC, differential and platelets—send to central lab

### **8.5 Day 4 (72 hours < 96 hours)**

For all patients, at 72 hours ( $\pm 1$  hour) from the time of randomization:

- Record vital signs
- Record concomitant medications
- Draw a blood sample for CBC, differential and platelets, chemistry profile, serum biomarkers—send to central lab
- Obtain a urine sample for biomarkers—send to central lab
- Record SpO2 and the FiO2 and time performed
- Calculate the Glasgow Coma Scale Score
- Record patient's pain using the PNRS
- Assess pain using the CPOT
- Perform AE/SAE assessment

For patients randomized to receive CM4620-IE:

- Start the administration of CM4620-IE (**4th dose**) 72 hours ( $\pm 1$  hour) from the start of dose administration on Day 1
  - Draw a blood sample for PK 30 minutes ( $\pm 15$  minutes) after completing the administration of CM4620-IE—send to central lab
  - Draw a blood sample for PK 8 hours ( $\pm 30$  minutes) after completing the administration of CM4620-IE—send to central lab

For all patients, at 84 hours ( $\pm 1$  hour) from the time of randomization:

- Record vital signs
- Draw a blood sample for CBC, differential and platelets—send to central lab

### **8.6 Day 5 (96 hours to < 120 hours)**

For all patients, at 96 hours ( $\pm 1$  hour) from the time of randomization:

- Record vital signs
- Record concomitant medications

- Draw a blood sample for CBC, differential and platelets, chemistry profile, serum biomarkers—send to central lab
- Obtain a urine sample for biomarkers—send to central lab
- Record SpO2 and the FiO2 and time performed
- Calculate the Glasgow Coma Scale Score
- If an ABG has already been performed as part of standard of care, record the pH, PaCO2, PaO2, SaO2 and the FiO2 at the time of draw
- Record patient's pain using the PNRS
- Assess pain using the CPOT
- Perform AE/SAE assessment

For patients randomized to receive CM4620-IE:

- Draw a blood sample for PK at 96 hours ( $\pm 1$  hour) from the start of dose administration on Day 1—send to central lab

For all patients, at 108 hours ( $\pm 1$  hour) from the time of randomization:

- Record vital signs
- Draw a blood sample for CBC, differential and platelets—send to central lab

**All patients will undergo a CECT of the pancreas on Day 5.**

- The CECT will be performed on Days 6 or 7 if unable to be performed on Day 5
- If the PI wishes to discharge a patient randomized to supportive care only before Day 5, a CECT should be performed prior to discharge
- If the PI wishes to delay the CECT beyond Day 7, the Medical Monitor should be contacted

## **8.7 Days 6 – 9**

For all patients who remain hospitalized, at 120 hours ( $\pm 1$  hour), 144 hours ( $\pm 1$  hour), 168 hours ( $\pm 1$  hour), 192 hours ( $\pm 1$  hour) from the time of randomization:

- Record vital signs
- Record concomitant medications
- Draw a blood sample for CBC, differential and platelets, chemistry profile, serum biomarkers—send to central lab
- Obtain a urine sample for biomarkers—send to central lab
- Record SpO2 and the FiO2 and time performed

- Calculate the Glasgow Coma Scale Score
- Record patient's pain using the PNRS
- Assess pain using the CPOT
- Perform AE/SAE assessment

## 8.8 Day 10

For all patients who remain hospitalized, at 216 hours ( $\pm 1$  hour) from the time of randomization:

- Record vital signs
- Record concomitant medications
- Perform limited physical examination
- Draw a blood sample for CBC, differential and platelets, chemistry profile, serum biomarkers—send to central lab
- Obtain a urine sample for biomarkers—send to central lab
- Record SpO2 and the FiO2 and time performed
- Calculate the Glasgow Coma Scale Score
- If an ABG has already been performed as part of standard of care, record the pH, PaCO2, PaO2, SaO2 and the FiO2 at the time of draw
- Record patient's pain using the PNRS
- Assess pain using the CPOT
- Perform AE/SAE assessment

For patients randomized to receive CM4620-IE:

- Draw a blood sample for PK at 216 hours ( $\pm 1$  hour) from the start of dose administration on Day 1—send to central lab

**If the patient is discharged after Day 5 and before Day 10, Day 10 procedures should be performed prior to discharge.**

## 8.9 Days 12 – 30

For all patients who remain hospitalized:

- Perform AE/SAE assessment if the patient is in the hospital every 48 hours starting on Day 12 until discharge, or until Day 30

- If the patient has been discharged from the hospital, contact the patient on Day 30 ( $\pm 2$  days) for SAE assessment and to determine if patient has been readmitted to the hospital (may be conducted by phone call to patient, LAR, primary MD, or chart review)

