For all 4 cohorts, a study physician or appropriately trained delegate will perform all assessments daily through Day 10, or until discharge if occurring earlier. After Day 10, and starting on Day 12, serious adverse events (SAEs) will be captured every 48 hours until Day 30 ( $\pm$  2 days), or until discharge if occurring earlier. Patients discharged prior to Day 30 will be contacted on Day 30 ( $\pm$  2 days) to capture SAEs and any re-admissions to the hospital. Patients will also be contacted on Day 90 ( $\pm$  7 days) to assess mortality.

CalciMedica may submit amendments to the protocol to modify the planned doses, the dosing schedule, the infusion time, the number of sites in the study, the total number of patients randomized in the study, the number of patients randomized in each cohort, the number of cohorts in each phase of the study, and/or the number of phases in the study for safety and/or efficacy considerations.

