### 5.2 Discharge Criteria

The patient randomized to receive CM4620-IE should remain in the hospital until all 4 doses of CM4620-IE have been administered, and a CECT of the pancreas has been performed. The suggested criteria for discharging patients from the hospital are:

- Abdominal pain has resolved
- Normal oral diet is tolerated
- There is no clinical or laboratory evidence of an infection

If the patient is ready to be discharged before all 4 doses of CM4620-IE have been administered or the CECT of the pancreas has been performed, the PI or treating physician should contact the Medical Monitor prior to discharging the patient.

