### 9.4 Recording Adverse Events

Recording of AEs must begin after randomization. All conditions present before randomization, including untoward medical events during Screening, should be documented as medical history. Documentation shall continue until the patient dies, the patient withdraws consent, or the patient’s participation in the study ends. Information to be collected includes:

- Type of event
- Date of onset
- Date of resolution
- Investigator-specified relationship to CM4620-IE and assessment of severity
- Seriousness
- Any action taken

While an AE is ongoing, changes in the severity (e.g., worsening and improving) should be noted in the source documents, but when documenting the AE, only the total duration and the greatest severity should be recorded in the case report form. AEs characterized as intermittent require documentation of onset and duration.

All AEs reported or observed during the study must be followed to resolution. Or, if not fully resolved, until the condition has stabilized, the patient dies, withdraws consent, or CalciMedica ends the trial whichever is first.

Adverse events resulting from concurrent illnesses, reactions to concurrent medications, or progression of disease states must also be reported. Pre-existing conditions (present before the start of the AE collection period) are considered concurrent medical conditions and should NOT be recorded as AEs. However, if the patient experiences a worsening or complication of such a concurrent condition, the worsening or complication should be recorded as an AE. Investigators should ensure that the AE term recorded captures the change in condition (e.g., “worsening of...”).

Each AE should be recorded to represent a single diagnosis. Accompanying signs (including abnormal laboratory test values or ECG findings) or symptoms should NOT be recorded as additional AEs. If a diagnosis is unknown, sign(s) or symptom(s) should be recorded as an AE(s).

Elective procedures (surgeries or therapies) performed to manage/treat conditions that existed prior to the patient enrolling in the trial should not be recorded as AEs but should be documented in the patient’s source documents. If a planned procedure is performed early (e.g., as an emergency) because the pre-existing condition worsens, the worsening condition should be captured as an AE.

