3.1.2 Primary endpoint

The primary endpoints of the study are related to safety, these include Adverse Events (AEs), Vital Signs (VS) and safety laboratory measures

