7.1.2 Analysis

The adverse events will be analyzed using frequencies and percent divided by SOC, and PT code using the TESS approach.

The vital signs will be presented using summary statistics by visit.

Safety laboratory parameters will be presented using shift tables.

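### Non-serious AEs are sought only in hospital and only drug patients are asked to stay for a minimum period, so the primary AE percentages could compare unequal observation windows

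*Protocol*

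**What the plan says.** **Endpoint and analysis.** SAP 3.1.2: "The primary endpoints of the study are related to safety, these include Adverse Events (AEs), Vital Signs (VS) and safety laboratory measures". SAP 7.1.2: "The adverse events will be analyzed using frequencies and percent divided by SOC, and PT code using the TESS approach". SAP 4.5 splits tables by treatment and dose group. The only analysis set the SAP defines (4.3.1) includes both arms. No AE cut-off, common window or observation time is given.

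**When AEs are asked about.** Protocol 8.2 to 8.8 place AE/SAE assessments at 12, 24, 48, 72 and 96 hours, then daily to Day 10 for those still in hospital. Section 8.9 continues: "Perform AE/SAE assessment if the patient is in the hospital every 48 hours starting on Day 12 until discharge, or until Day 30". For discharged patients, 8.9 and schedule footnote b limit the Day 30 contact to SAEs and readmission. Section 8.10 and footnote c limit Day 90 to mortality. Section 9.4 is broader: "Documentation shall continue until the patient dies, the patient withdraws consent", or participation ends.

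**Who stays.** Section 5.2: "The patient randomized to receive CM4620-IE should remain in the hospital until all 4 doses of CM4620-IE have been administered", and until the CT scan is done. Earlier discharge calls for contact with the Medical Monitor. Section 8.6 on controls: "If the PI wishes to discharge a patient randomized to supportive care only before Day 5, a CECT should be performed prior to discharge".

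**Two internal conflicts.** Section 3.1 says "After Day 10, and starting on Day 12, serious adverse events (SAEs) will be captured every 48 hours until Day 30", whereas 8.9 asks for AEs and SAEs over the same period. The rule following 8.8 says "If the patient is discharged after Day 5 and before Day 10, Day 10 procedures should be performed prior to discharge", whereas schedule footnote h applies those procedures to any discharge before Day 10.

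**The concern.** The window for soliciting non-serious AEs closes at discharge, and only one arm has a stated minimum stay. A control who is well by Day 3 can go home and is not asked again about non-serious events. A drug patient in the same condition is asked to stay for the remaining doses and the scan, and is assessed on each of those days. With identical true AE rates, the drug patient has more chance of a recorded event.

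The controls are the comparator for background events of pancreatitis, so a shorter control window could inflate the apparent excess on drug in a primary endpoint. Separately, delayed non-serious events in discharged patients of either arm are not sought, although Protocol 1.5 and 1.6 describe prolonged residual drug levels.

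**Working it through.** **1. Plan's own figures.** Cohorts: 4 + 4 + 8 + 8 = 24, matching Protocol 10.1. Allocation 3:1 within cohorts gives 3 + 3 + 6 + 6 = 18 drug and 1 + 1 + 2 + 2 = 6 control. One control is 1/6 = 16.7 points and one drug patient is 1/18 = 5.6 points. The documents give no AE rate and no expected stay.

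**2. Minimum stay.** On drug, the fourth dose starts about 72 h after the first and runs 4 h, so it ends at about 76 h. The scan is nominally on Day 5 (96 to <120 h). Controls have no minimum stay. A control leaving at 60 h has had 3 scheduled AE assessments (12, 24, 48 h). A drug patient kept to 96 h has had 5.

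**3. Illustration.** Assume the same constant rate r in both arms and observation for t days, so P(at least one AE) = 1 − exp(−r·t). Rates and discharge times are assumptions. For example, at r = 0.2, 3 days gives 1 − exp(−0.6) = 45.1% and 5 days gives 1 − exp(−1.0) = 63.2%, a gap of 18.1 points.

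Gap, drug minus control, in percentage points:

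| Discharge pattern | r = 0.1 | r = 0.2 | r = 0.3 |
|---|---|---|---|
| Nobody ready before the drug-arm minimum | 0 | 0 | 0 |
| One third ready: 3 v 5 days; rest equal and contributing no gap | 4.5 | 6.0 | 6.1 |
| One third ready: 2 v 4 days; rest 6 days in both arms | 4.9 | 7.4 | 8.3 |
| All: 3 v 4 days | 7.0 | 9.9 | 10.5 |
| All: 3 v 5 days | 13.4 | 18.1 | 18.3 |
| All: 2 v 4 days | 14.8 | 22.1 | 24.8 |

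The second row is one third of the fifth (for example 13.4/3 = 4.5). In the fifth row the percentages are 25.9 v 39.3, 45.1 v 63.2 and 59.3 v 77.7.

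**4. If the rate falls before discharge.** Take 0.2 per day for 3 days, then 0.05 per day for 2 held days. Control: 1 − exp(−0.6) = 45.1%. Drug: 1 − exp(−0.7) = 50.3%. The gap is 5.2 points instead of 18.1.

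**5. Per-patient-day rates under the same assumption.** Control: 0.60/3 = 0.20. Drug: 0.70/5 = 0.14. With no drug effect, the drug now looks safer, because low-risk held days enlarge its denominator.

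**The case against.** The strongest objection is that the plan creates only a possibility of unequal windows. The hold in 5.2 is advisory and has a Medical Monitor route for earlier discharge. The default for every patient, controls included, is a Day 5 scan, and the suggested discharge criteria are otherwise common to both arms. Patients who are held are by those criteria free of pain, eating and without infection, so applying the acute-phase AE rate to their held days overstates the effect. SAEs are sought to Day 30 in both arms. Both dose groups share one discharge rule, so the hold does not distort the comparison between doses. The study is descriptive, and a gap of 4 to 8 points is less than half of one control patient. All of this stands, and it limits the size and certainty of the point.

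Other parts stand only partly. The schedule marks AE/SAE evaluation at Days 30 and 90, and 9.4 keeps recording open, so a volunteered event could be entered; but footnotes b and c narrow those contacts, and none seeks non-serious events after discharge. Phase 1 recipients in four dose groups were followed for 365 days with no serious, moderate or severe AE. They were healthy subjects, and the second phase here targets a mean exposure 30% above that of the first, which is set to resemble the highest SAD and MAD groups. Footnote h would give an early-discharged control a final AE assessment, but the text after 8.8 would not.

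A reader might infer that the plan builds in a spurious drug excess of 13 to 18 points. The documents do not support that: it needs every control to leave at 3 days, every drug patient at 5, and a constant rate throughout. Nor do the Day 12 to 30 rules themselves favour an arm, since they apply to both alike.

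**Conclusion.** The point holds conditionally. Three features are in the text: non-serious AEs solicited only in hospital, a minimum stay asked of drug patients only, and crude percentages by arm for a primary endpoint. Together they allow unequal windows for patients ready to leave early.

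The size cannot be determined from the documents. Under equal constant rates of 0.1 to 0.3 per day it runs from 0, through about 4 to 8 points if one third are ready early, to 13 to 18 points in the all-patients 3 v 5 day case. Other all-or-nothing patterns move that upper figure, as the table shows. Falling rates shrink the gap, and a shorter stay on drug could reverse it, so the plan could inflate the AE excess on drug but does not necessarily do so. SAE comparisons to Day 30 are not affected by this mechanism.

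The two textual conflicts (3.1 against 8.9, and the 8.8 rule against footnote h) exist whatever the size, and need reconciling. The changes are cheap and should be made.

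**What to change.** 1. **Day 30 contact.** In Protocol 8.9, 3.1, the synopsis and schedule footnotes a and b, have the existing contact for discharged patients ask for all AEs and SAEs since discharge. Reconcile 3.1 (SAEs only) with 8.9 (AEs and SAEs) for in-patients after Day 10. SAP 3.2 repeats the 3.1 wording and should follow.
2. **Discharge assessment.** Reconcile the rule after 8.8 with footnote h, so that every discharge before Day 10 has at least a final AE/SAE assessment.
3. **SAP 7.1.2.** Report AEs by arm over a common window from randomization, for example to Day 30, plus a common early window fixed before database lock. Show events first reported at the Day 30 contact separately. Tabulate in-hospital observation time by arm. Treat any per-patient-day rate as supplementary only, for the reason in step 5 of the working.

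**Cost.** Protocol wording, a few more questions at a contact that already takes place, and a small number of tables. Dosing and discharge rules are untouched. If item 2 is resolved by adopting the full Day 10 set, it also brings central-laboratory samples, an examination and PK sampling, which footnote h already implies; an AE/SAE assessment alone costs little. The downside is that non-serious events recalled at Day 30 are less precise than those recorded in hospital, hence the separate display.
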